9.3 Analysis of Laboratory Data

Data collected from central and local laboratories, including additional laboratory testing due to an SAE, will be used in all analyses, except for Baseline where SAE-related laboratory assessments on or before the first dose of study drug will be excluded. The clinical laboratory tests defined in the protocol operations manual (e.g., hematology and clinical chemistry) will be summarized.

Each laboratory variable will be summarized for all time points (starting with Baseline) with the number of non-missing observations, mean and standard deviation, median, minimum and maximum. Mean change from baseline to each applicable post-baseline visit will be summarized for selected laboratory variables, with the number of observations, baseline mean, and visit mean. The change from baseline mean, standard error, and 95% confidence interval will be presented for the mean change from baseline within each treatment group and difference between each elagolix group and placebo. Selected laboratory variables are lipid variables, liver variables (alkaline phosphatase, ALT, AST, bilirubin), hemoglobin, hematocrit, platelet count, and red blood cell (RBC) count.

Changes in laboratory parameters will be tabulated using shift tables either by NCI CTC criteria or categorized as low, normal, or high based on the normal ranges of the

laboratory used for each sample. A shift table from baseline either to the worse value (based on NCI CTC criteria) during treatment or to minimum and maximum value (based on normal range), will be created. A similar shift table will be provided to summarize shifts from baseline to the final post-baseline value.

Laboratory abnormalities meeting CTCAE criteria grade 3 and 4 will be summarized.

The number and percentage of subjects meeting the following criteria will be summarized at Baseline and each relevant visit by treatment group in the Treatment Period:

- Total cholesterol: ≤ 300 , $> 300 - \leq 400$, $> 400 - \leq 500$, and > 500 mg/dL
- HDL-C: < 40 and ≥ 40 mg/dL
- LDL-C: < 130 , $\geq 130 - < 160$, $\geq 160 - < 190$, and ≥ 190 mg/dL
- TG: ≤ 150 , $> 150 - \leq 300$, $> 300 - \leq 500$, $> 500 - \leq 1000$, and > 1000 mg/dL

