In addition, the number and percentage of subjects who have potentially clinically significant (PCS) lipid values meeting the following criteria any time during the Treatment Period will be summarized by treatment group: Listings will be provided to summarize subject-level laboratory data for subjects meeting PCS criteria.

- Total cholesterol > 200 mg/dL
- LDL-C > 130 mg/dL
- LDL-C > 160 mg/dL
- HDL-C < 40 mg/dL
- TG > 150 mg/dL

The number and percentage of subjects in each treatment group with maximum on treatment laboratory values meeting the following criteria compared to the upper limit of normal (ULN) will be summarized by treatment group to assess potential hepatotoxicity.

- ALT $\geq 3 \times$ ULN and total bilirubin $\geq 2 \times$ ULN
- AST $\geq 3 \times$ ULN and total bilirubin $\geq 2 \times$ ULN

- ALT and AST $\geq 3 \times$ ULN and total bilirubin $\geq 2 \times$ ULN
- ALT $\geq 3 \times$ ULN and total bilirubin $< 2 \times$ ULN
- AST $\geq 3 \times$ ULN and total bilirubin $< 2 \times$ ULN
- ALT and AST $\geq 3 \times$ ULN and total bilirubin $< 2 \times$ ULN
- ALT $\geq 3 \times$ ULN and total bilirubin $\geq 1.5 \times$ ULN
- AST $\geq 3 \times$ ULN and total bilirubin $\geq 1.5 \times$ ULN
- ALT and AST $\geq 3 \times$ ULN and total bilirubin $\geq 1.5 \times$ ULN
- ALT $\geq 3 \times$ ULN, $\geq 5 \times$ ULN, $\geq 10 \times$ ULN, $\geq 20 \times$ ULN
- AST $\geq 3 \times$ ULN, $\geq 5 \times$ ULN, $\geq 10 \times$ ULN, $\geq 20 \times$ ULN
- Total bilirubin $\geq 1.5 \times$ ULN, $\geq 2.0 \times$ ULN

The maximum ratio relative to the ULN is used to determine if subjects met the criteria listed above. The ALT, AST, and total bilirubin values do not need to be concurrent in order to meet the defined criteria. For ALT, AST, and total bilirubin, a subject is counted if the post-baseline laboratory value during the Treatment Period meets the above criteria regardless of Baseline laboratory value (i.e., the post-baseline laboratory value does not need to be worse than Baseline laboratory value).

A listing of all ALT, AST, total bilirubin, and alkaline phosphatase values will be provided for each subject who met any of the criteria defined above.

The following plots will be generated: peak AST vs. peak bilirubin; peak ALT vs. peak bilirubin.

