9.4 Analysis of Vital Signs and Weight

Vital sign variables include sitting systolic blood pressure and sitting diastolic blood pressure.

Each vital sign variable and weight will be summarized for all time points (starting with Baseline) with the number of non-missing observations, mean and standard deviation, median, minimum and maximum. Mean change from baseline to each applicable post-

baseline visit will be summarized for each vital sign variable, with the number of observations, baseline mean, and visit mean. The change from baseline mean, standard error, and 95% confidence interval will be presented for the mean change from baseline within each treatment group and difference between each elagolix group and placebo.

The number and percentage of subjects who have potentially clinically significant (PCS) vital sign and weight values meeting the following criteria will be summarized by treatment group. All increase/decrease is calculated from Baseline to a post-baseline visit in the Treatment Period.

- Diastolic blood pressure
 - ≤ 50 mmHg and ≥ 15 mmHg decrease
 - > 90 mmHg and ≥ 15 mmHg increase
 - ≥ 100 mmHg
- Systolic blood pressure
 - ≤ 90 mmHg and ≥ 20 mmHg decrease
 - ≥ 140 mmHg and ≥ 20 mmHg increase
 - ≥ 160 mmHg
- Weight
 - $\geq 5\%$ decrease
 - $\geq 7\%$ increase.

Listings will be provided to summarize subject-level vital sign and weight data for subjects meeting PCS criteria.

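### The table of potentially clinically significant lipid values does not separate women who newly meet a cut-off from those who already met it at Baseline

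*SAP*

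**What the plan says.** SAP 9.3 (Analysis of Laboratory Data) plans a lipid table in which women "who have potentially clinically significant (PCS) lipid values meeting the following criteria any time during the Treatment Period will be summarized by treatment group". The criteria are total cholesterol > 200, LDL-C > 130, LDL-C > 160, HDL-C < 40 and triglycerides > 150 mg/dL. None has a change component or a condition on the Baseline value.

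Other parts of the SAP do address baseline:

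- For ALT, AST and total bilirubin, 9.3 says explicitly that "the post-baseline laboratory value does not need to be worse than Baseline laboratory value". There is no matching sentence for lipids, so counting women who already met a lipid cut-off is the natural reading of silence and not a stated rule.
- In 9.4 four of the six blood-pressure criteria combine a level with a change, for example "≥ 140 mmHg and ≥ 20 mmHg increase", and both weight criteria are changes. The section adds: "All increase/decrease is calculated from Baseline to a post-baseline visit in the Treatment Period". The other two (diastolic ≥ 100, systolic ≥ 160 mmHg) are level only.
- A separate set of lipid categories in 9.3 "will be summarized at Baseline and each relevant visit by treatment group in the Treatment Period".
- 9.3 also plans mean lipid change with 95% confidence intervals, within group and against placebo, and shift tables by NCI CTC grade or laboratory normal range. SAP 8.5.5 plans an ANCOVA of change in each of the four lipids with the baseline value as covariate.

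**The concern.** A table of potentially clinically significant values is normally read as showing what happened on treatment. Here a woman with total cholesterol of 210 mg/dL before the first dose and 210 mg/dL at Week 4 counts the same as one who rose from 170 to 210.

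Women already meeting a cut-off can be enrolled. Protocol 5.1 sets no lipid limit and excepts disease-associated findings from its general laboratory exclusion. It allows BMI up to 38 kg/m², and Protocol Table 1 requires lipid-lowering agents to be washed out.

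At stake is whether this safety table can show new lipid abnormalities in comparisons of 20 women with 30. Efficacy conclusions are not affected.

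**Working it through.** **1. Does another planned table count new crossings?**

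| Planned output | Uses Baseline? | Counts new crossings of these cut-offs? |
|---|---|---|
| Categories by visit (9.3) | Baseline column shown | No. Counts are marginal at each visit. HDL-C and triglycerides share the cut-offs; LDL-C is split at ≥ 130 and ≥ 160, not > 130 and > 160; for total cholesterol the lowest category is "Total cholesterol: ≤ 300", so there is no Baseline count at "Total cholesterol > 200 mg/dL" |
| Shift tables (9.3) | Yes | No. CTC grades or normal ranges |
| Mean change against placebo (9.3) | Yes | No. Average effect |
| ANCOVA of change (8.5.5) | Yes | No. Average effect |
| Subject listings (9.3) | Not specified | No. At best, a reader could rebuild the count by hand |

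**2. Size of the dilution.** The SAP states no figure for this table, so there is none to reproduce. Group sizes (20 per elagolix arm, 30 placebo) come from SAP 2.4. Every rate below is an assumption.

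Let b be the share meeting a cut-off at Baseline, r the share of those who meet it again on treatment, and q1 and q0 the new-occurrence rates on drug and placebo.

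- Any-time rate = b·r + (1 − b)·q
- With r equal in both arms, any-time difference = (1 − b)(q1 − q0)
- Share of counted women who already met the cut-off = b·r / [b·r + (1 − b)·q]

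Take r = 0.85, q1 = 0.25 and q0 = 0.05, so the excess in new occurrence is 20 points. At b = 0.30:

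- drug: 0.30 × 0.85 + 0.70 × 0.25 = 0.43
- placebo: 0.30 × 0.85 + 0.70 × 0.05 = 0.29
- difference: 14 points = 0.70 × 20
- share already meeting it on drug: 0.255 / 0.43 = 59%

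| b | Difference shown | Share of counted elagolix women already meeting it | Chance of no or reversed excess: any-time count | Same: women not meeting it at Baseline |
|---|---|---|---|---|
| 20% | 16 points | 46% | 12% | 4% |
| 30% | 14 points | 59% | 17% | 5.5% |
| 50% | 10 points | 77% | 26% | 11% |

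The last two columns are for one comparison of 20 with 30 women.

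**3. Sensitivity to persistence.** If r differs by arm, the difference gains a term b(r1 − r0). With r1 = 0.95 and r0 = 0.75:

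- b = 0.30: 0.70 × 20 + 0.30 × 20 = 20 points
- b = 0.50: 0.50 × 20 + 0.50 × 20 = 20 points

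The dilution is gone. The chance of no or reversed excess in the any-time count falls to 8% at b = 0.30 and 9% at b = 0.50. At b = 0.50 the restricted count then does slightly worse (10.7% against 8.9%).

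**The case against.** The strongest reply is that the lipid effect is already well covered. The ANCOVA in 8.5.5 adjusts for the baseline value, 9.3 gives mean change against placebo with confidence intervals, and the by-visit categories show Baseline counts by arm at the same or nearly the same cut-offs for HDL-C, triglycerides and LDL-C. Any-time counting is also used elsewhere in the SAP: the liver criteria disregard baseline by express rule and two blood-pressure criteria are level only. The table is descriptive and no test is planned for it. All of this stands, and it limits the point to one table.

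Three stronger readings are tempting, and the documents do not support them.

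- *The table largely reports baseline dyslipidaemia.* No prevalence, persistence or new-occurrence rate is given. Under the rates above, the share already meeting the cut-off is 46% on drug at b = 20%, below half. It will also differ by criterion, since LDL-C > 160 cannot be met more often than LDL-C > 130.
- *Chance imbalance at baseline dominates the comparison.* Its share of the variance of the difference is [b(1 − b)(r − q1)²/20 + b(1 − b)(r − q0)²/30] divided by the total binomial variance. At b = 0.30 that is 0.00826 / 0.01912 = 43%; at b = 0.50 it is 0.00983 / 0.02063 = 48%. It is substantial but under half.
- *A lipid signal would be hidden from the report.* The mean-change and ANCOVA results would still show an average effect.

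The liver rule is only a partial precedent. It is written out for three analytes, whereas for lipids the SAP is silent.

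**Conclusion.** The point holds for this table. As worded, it mixes new and pre-existing abnormalities, and no other planned summary table separates them at these cut-offs. With similar persistence across arms, the between-arm difference is reduced by the factor (1 − b), to 14 points of a 20-point excess at b = 30% and 10 points at 50%. That size rests on assumed rates and on equal persistence; if the drug keeps already abnormal women abnormal, the reduction is smaller or absent. This is a minor, worthwhile improvement to a descriptive safety table.

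**What to change.** In SAP 9.3, for each lipid cut-off:

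1. Keep the all-subject any-time count.
2. Beside it, give the number and percentage of women who newly meet the criterion. The denominator is women who did not meet it at Baseline and have at least one post-baseline value in the Treatment Period.
3. Add the Baseline count by arm at each cut-off, including total cholesterol > 200 mg/dL.

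Keeping both counts matters, because neither is better under every persistence assumption. The data already exist: Operations Manual 2.1 and 2.2 schedule lipid panels at Screening and Baseline.

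The cost is about a sentence of SAP text, a programming filter and extra columns. The added count has smaller denominators: at b = 30%, about 0.70 × 20 = 14 women per elagolix arm and 0.70 × 30 = 21 on placebo. Trial conduct does not change.

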9.4 Analysis of Vital Signs and Weight

Vital sign variables include sitting systolic blood pressure and sitting diastolic blood pressure.

Each vital sign variable and weight will be summarized for all time points (starting with Baseline) with the number of non-missing observations, mean and standard deviation, median, minimum and maximum. Mean change from baseline to each applicable post-

baseline visit will be summarized for each vital sign variable, with the number of observations, baseline mean, and visit mean. The change from baseline mean, standard error, and 95% confidence interval will be presented for the mean change from baseline within each treatment group and difference between each elagolix group and placebo.

The number and percentage of subjects who have potentially clinically significant (PCS) vital sign and weight values meeting the following criteria will be summarized by treatment group. All increase/decrease is calculated from Baseline to a post-baseline visit in the Treatment Period.

- Diastolic blood pressure
 - ≤ 50 mmHg and ≥ 15 mmHg decrease
 - > 90 mmHg and ≥ 15 mmHg increase
 - ≥ 100 mmHg
- Systolic blood pressure
 - ≤ 90 mmHg and ≥ 20 mmHg decrease
 - ≥ 140 mmHg and ≥ 20 mmHg increase
 - ≥ 160 mmHg
- Weight
 - $\geq 5\%$ decrease
 - $\geq 7\%$ increase.

Listings will be provided to summarize subject-level vital sign and weight data for subjects meeting PCS criteria.

9.5 Other Safety Analyses

9.5.1 Columbia Suicide Severity Rating Scale (C-SSRS)

The C-SSRS data will be summarized as observed by treatment group.

The C-SSRS – Baseline/Screening measured at Day 1 will be considered as Baseline C-SSRS. Baseline C-SSRS will be summarized by treatment group. Other analysis of

C-SSRS will only include subjects who have at least 1 post-baseline C-SSRS measurement, regardless of whether they had a baseline C-SSRS measurement. The number of subjects with suicidal ideation, suicidal behavior, and self-injurious behavior without suicidal intent at each scheduled assessment during Treatment Period will be summarized. In addition, this table will be repeated for providing a summary of lifetime outcomes and past year outcomes at screening and Day 1. No statistical test will be performed.

The number of subjects with suicide-related treatment-emergent events based on the C-SSRS during Treatment Period will be summarized. No statistical tests will be performed.

A listing of subjects with suicidal ideation, suicidal behavior, or self-injurious behavior without suicidal intent based on the C-SSRS during treatment period will be provided.

9.5.2 Bone Mineral Density

All analyses and summaries of bone mineral density (BMD) will be performed for each segment, i.e., femoral neck, lumbar spine, and total hip. For subjects who had a right-side scan performed (rare instances), their data for right femoral neck and right femoral total hip will be included in the analysis with the data for the left femoral neck and left total hip, respectively (available for the majority of subjects). If more than one scan is reported for an anatomical segment within an analysis window, the worse (the lower value) of the multiple measurements will be used for analysis for each anatomical segment. The analyses below will exclude subjects who switch machine manufacturer types between baseline and post-baseline.

A continuous summary of BMD at Baseline and Month 6 will be provided by treatment group. This summary will include the mean, SD, median, minimum, and maximum.

The analysis of percent change from baseline in BMD during the Treatment Period will be based on an ANCOVA model with treatment as the main effect and baseline value of

corresponding parameter as a covariate. Each elagolix group will be compared to placebo.

The number and percentage of subjects with percent change from Baseline to Month 6 during the Treatment Period in mutually exclusive categories of BMD decrease: $\leq 0\%$, $> 0\% - \leq 1.5\%$, $> 1.5\% - \leq 3\%$, $> 3\% - \leq 5\%$, $> 5\% - < 8\%$, and $\geq 8\%$ will be summarized by treatment group. The comparison between each elagolix group and placebo will be made using Fisher's exact test.

A listing of subjects with BMD decrease from baseline $\geq 8\%$ will be provided.

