#### Rescreening

Subjects who screen fail for this study may be rescreened. Prior to rescreening a subject, the investigator should consult with the AbbVie Therapeutic Area Medical Director (TA MD). The TA MD will determine which procedures will need to be repeated if the subject was a screen failure for this study or another AbbVie elagolix study. The subject must re-consent and meet all eligibility criteria at the time of rescreening to qualify for the study.

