#### Dual Energy X-ray Absorptiometry (DXA)

DXA scans of the lumber spine, femoral neck, and total hip will be performed at the time points specified in Section 2. Site training and qualifications, which include assessment of instruments, will be evaluated/approved by the central reader prior to screening of the first subject. Instructions on calibration and standardization of instruments and any additional required information will be specified in a manual from the central reader that will be provided to all study sites. Sites will need to obtain approval from the central reader prior to initiating study scans.

The screening DXA scan will be sent to the central reader to determine eligibility and serve as the baseline scan for subject management.

During the Treatment Periods, DXA scans will be performed for all subjects at Week 24 and will be submitted to the central reader for review and analysis. DXA scans will only be performed at the PD Visit if the subject has received study drug for at least 12 weeks.

DXA scans will be performed by qualified technologist/radiologists at the site or affiliated imaging facility using GE Lunar or Hologic equipment and per the acquisition guidelines provided by the Central Imaging Core Lab (central reader). The DXA technologist/radiologist or designee for each investigative site

should electronically submit the subject's DXA images to the central reader for review and analysis following acquisition. The central reader will be blinded to the subject's treatment assignment, but not to the corresponding time point.

Subject eligibility will be made based on the central reader review. Sites will receive reports from the central reader that detail the results (including Z-scores and bone mineral density (BMD) % change from Baseline, as applicable) of the DXA scans performed.

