8.0 Efficacy Analyses

8.1 General Considerations

All efficacy analyses will be conducted using the FAS. Unless otherwise specified, each elagolix dose group will be compared to placebo. All statistical tests will be conducted at an alpha level of 0.1 (two-sided). A test will be deemed significant if the P value rounded to three decimal places is less than or equal to 0.1 unless otherwise specified.

Unless otherwise specified, categorical data will be summarized by frequencies and percentages for each treatment group and overall; continuous data will be summarized by the mean, standard deviation, median, minimum, and maximum for each treatment group and overall. For the analyses of change from baseline, the within-group changes will be summarized with the mean, standard deviation, and the median; between-group differences will be summarized with the mean, standard error, P value, and the 90% CIs.

Baseline refers to the last non-missing value obtained prior to or on Study Day 1.

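### SAP 9.5.2 tests six ordered categories of BMD loss with Fisher's exact test, which ignores the order and costs power; the repeat-scan rule also leaves Baseline unclear

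*SAP*

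**What the plan says.** SAP 9.5.2 sets out two between-group analyses of BMD at the femoral neck, lumbar spine and total hip.

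- Continuous: "The analysis of percent change from baseline in BMD during the Treatment Period will be based on an ANCOVA model" with treatment and the baseline value, each elagolix group against placebo.
- Categorical: percent change to Month 6 is sorted into six bands of decrease, cut at 0, 1.5, 3, 5 and 8%. "The comparison between each elagolix group and placebo will be made using" Fisher's exact test. The SAP does not say whether this is one test on the 2×6 table or a test per category. Subjects with a loss of 8% or more are also listed.

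On repeat scans the same section says "If more than one scan is reported for an anatomical segment within an analysis window, the worse (the lower value) of the multiple measurements" is the one to be analysed. The rule refers to an analysis window, but the SAP defines no DXA window.

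Two other places bear on which scan is Baseline. SAP 8.1, under efficacy, says "Baseline refers to the last non-missing value obtained prior to or on Study Day 1". The Operations Manual, in its DXA section (3.17), says "The screening DXA scan will be sent to the central reader to determine eligibility and serve as the baseline scan for subject management". The safety general considerations (SAP 9.1) give no baseline rule.

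One pre-dose scan is planned, and "DXA scans will be performed for all subjects at Week 24". A second pre-dose scan could arise through rescreening (Protocol 4.1), where "The TA MD will determine which procedures will need to be repeated".

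**The concern.** The six bands form a scale from no loss to severe loss. If elagolix lowers BMD, subjects should move along that scale in one direction. Fisher's test on a 2×6 table spreads its sensitivity over every possible difference in pattern, including ones with no clinical meaning, such as more subjects in alternate bands. With about 20 subjects per elagolix group, the SAP can ill afford that. A non-significant result in this table could be read as reassurance when the test was weak.

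The repeat-scan rule raises a smaller question. A lower value is the worse one only after treatment starts. At Baseline, a lower value reduces the calculated loss. Nothing in SAP 9.5.2 confines the rule to post-baseline scans.

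**Working it through.** **The plan's own figure.** The documents state no power for BMD. The only stated power is at least 85% for the primary endpoint (SAP 2.4: 10% versus 50%, 30 versus 20 subjects, two-sided 0.05, Pearson chi-square). Pooled rate = (3 + 10)/50 = 0.26. Null SE = √[0.26 × 0.74 × (1/30 + 1/20)] = 0.1266. Alternative SE = √(0.09/30 + 0.25/20) = 0.1245. Power = Φ[(0.40 − 1.96 × 0.1266)/0.1245] = Φ(1.22) = 88.9%. The figure holds, but it says nothing about BMD.

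**Fisher against an ordered test.** From the documents: 20 versus 30 subjects (SAP 2.4), alpha 0.05 for safety (SAP 9.1) and the five cut-points (SAP 9.5.2). Assumed, because the documents give none: normally distributed percent change, SD 2–3%, placebo mean 0, extra mean loss on elagolix of 1–3 points, and a single test on the 2×6 table. There were 1,500 simulated trials per row, so the Monte Carlo SE is at most √(0.25/1500) = 1.3 points. The t-test stands in for the ANCOVA.

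| SD (%) | Extra loss (points) | Fisher 2×6 | Wilcoxon on the six bands | Gain | t-test on continuous change |
|---|---|---|---|---|---|
| 2.0 | 1 | 22.7% | 31.5% | 8.8 | 38.8% |
| 2.0 | 1.5 | 47.7% | 63.5% | 15.8 | 70.9% |
| 2.0 | 2 | 72.4% | 88.1% | 15.7 | 91.1% |
| 2.0 | 3 | 97.9% | 99.7% | 1.8 | 99.9% |
| 2.5 | 1 | 15.5% | 22.1% | 6.6 | 25.5% |
| 2.5 | 1.5 | 32.9% | 46.5% | 13.6 | 52.2% |
| 2.5 | 2 | 53.0% | 71.6% | 18.6 | 78.6% |
| 2.5 | 3 | 88.9% | 96.7% | 7.8 | 98.3% |
| 3.0 | 1 | 12.5% | 16.5% | 4.0 | 19.1% |
| 3.0 | 1.5 | 22.9% | 34.5% | 11.6 | 38.9% |
| 3.0 | 2 | 37.8% | 56.5% | 18.7 | 62.7% |
| 3.0 | 3 | 71.1% | 89.0% | 17.9 | 93.9% |

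With no true difference, Fisher rejected in 4.5–5.8% of trials and Wilcoxon in 4.4–5.3%. Both are valid, so the cost is power alone. If fewer subjects have a Month 6 scan, say 15 versus 23, the gap remains: 58.3% versus 75.8% for SD 2% and a 2-point loss.

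**Repeat scans.** For two scans with independent normal error of SD σ, the expected lower value is the true value minus σ/√π = 0.56σ. With an assumed precision error of 1.0% this is 0.56 points, with 1.5% it is 0.85 points, and with 2.5% it is 1.41 points. For a true change of −3.0% and a precision error of 1.5%, the mean calculated change is:

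- single scans at both times: −2.98%
- lower of two at Baseline only: −2.15%
- lower of two at Month 6 only: −3.80%
- lower of two at both times: −2.98%

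For the 8% listing, take a subject whose true loss is exactly 8% and whose scan error is proportional. With single scans she is listed half the time. With two Baseline scans she is listed only if the Month 6 error is the lowest of three, a chance of 1/3. With two Month 6 scans and one Baseline scan the chance is 2/3.

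The shift in a group mean is the share of subjects with repeat Baseline scans times σ/√π. For shares of 5–20% and precision errors of 1.0–2.5% it runs from 0.05 × 0.56 = 0.03 to 0.20 × 1.41 = 0.28 points.

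**The case against.** **On Fisher's test.** The category table supplements the ANCOVA, which uses the continuous change. In the simulation the continuous test beats even the ordered test (78.6% versus 71.6% at SD 2.5%, 2-point loss). Fisher's test is valid, there is no Type I error control (SAP 10.0), and no stated conclusion rests on this p-value. All of that stands and keeps the point minor. It is still no reason to use the weaker test where a between-group test is planned. The power figures assume the 2×6 layout, which the SAP leaves open.

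**On repeat scans.** A reader might infer that the SAP lowers Baseline and so hides bone loss. The documents do not say so. SAP 9.5.2 never states that the rule sets Baseline, and SAP 8.1 and the Operations Manual point to the last or screening scan. What remains is an ambiguity: SAP 8.1 sits in the efficacy section, the Operations Manual sentence concerns subject management, and no DXA window is defined.

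A reader might also infer that the rule makes a difference between arms harder to detect. Screening scans precede randomization, so any shift is expected to be equal across arms. In a simulation with a 2-point extra loss, SD 2.5% and precision error of 1.0–1.5%, the ANCOVA difference stayed at −2.00 to −2.02 points and power at 76–81%, whether 0, 10, 20 or 100% of subjects had the lower of two Baseline scans.

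Nor does either choice affect how bone-related adverse events of special interest are found. SAP Appendix A identifies them by a standardized MedDRA query.

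**Conclusion.** The point on Fisher's test holds. Ignoring the order of the six categories costs about 2 to 19 points of power over the range examined, and most where power is moderate. This rests on the assumed SDs, effect sizes, normality and 2×6 layout. It does not mean that the trial lacks a sensitive BMD comparison, because the planned ANCOVA provides one.

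The repeat-scan rule is a secondary matter of wording. Under the least favourable reading, and only for a subject with repeat scans at Baseline and a single Month 6 scan, loss is understated by about 0.6–0.8 points at an assumed precision error of 1–1.5%. That would affect within-arm change, category counts and the 8% listing, but not, on average, the between-arm difference. With one scan planned at each time, repeats should be uncommon, though the documents give no rate. Both parts are minor.

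**What to change.** In SAP 9.5.2:

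1. Replace Fisher's exact test on the BMD categories with an exact Wilcoxon test or a CMH row-mean-score test on the ordered categories, each elagolix group against placebo.
2. Define the DXA analysis windows and state that Baseline is the last acceptable pre-dose scan; or use the mean of repeat scans at both Baseline and Month 6. The mean is cleaner. Keeping the lower-value rule after baseline alone would overstate loss for subjects rescanned then (−3.80% against −2.98% above), at a stage when rescanning could differ by arm.

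The cost is a few lines of SAP text and a change of test option in the program. No new data, visits or subjects are needed.
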